2.6 Study Product

INSIGHT 006: FLU-IVIG

For this study, the FLU-IVIG was manufactured by Emergent BioSolutions, Winnipeg, Canada (formerly Cangene) under contract to the United States National Institute of Allergy and Infectious Diseases (NIAID), National Institutes of Health (NIH), using high titer plasma collected from volunteers. Emergent BioSolutions also manufactured the product used in the pilot study (INSIGHT 005: FLU-IVIG Pilot). The IVIG product used in this trial is manufactured according to Good Manufacturing Practices (GMP) from human plasma collected under IND at sites that are FDA-registered or licensed to perform this function. Based on the current Investigator's Brochure (Version 5.0), the plasma used in this IVIG product meet the following criteria prior to being used for manufacture:

- Negative Aniti-HIV 1 / 2
- Negative Anti-HTLV 1 / 2
- Negative Anti-HCV
- Negative HBsAg
- Negative serologic test for syphilis
- Negative HIV NAT
- Negative HCV NAT
- Negative WNV NAT
- Negative Hepatitis A virus NAT
- Negative Hepatitis B virus NAT
- Negative Parvovirus B19 NAT

Any updates to the criteria will be documented in the next version of the Investigator's Brochure.

All tests are performed by commercially available assays.

The lots of IVIG are tested at manufacture and periodically (at 3, 6, 9, 12, 18, 24, 36, and 48 months post-manufacture) for contemporary strains of influenza (as defined by the strains recommended by the WHO for the seasonal influenza vaccine). IVIG is manufactured in batches, and lot-to-lot variations in antibody titers may occur. The

strain-specific HAI results by lot are included in the Investigator's Brochure (IB), however, it is anticipated that the IVIG to be used in this study has the following average HAI titers:

A/H1N1 = 1:640

INSIGHT 006: FLU-IVIG

- A/H3N2 = 1:640
- B = 1:160

If any new strains of influenza emerge through a season, additional HAI testing will be conducted against the new strain, when able, to document expected activity towards the new strain.

The anticipated HAI titer levels in participants following infusion were estimated as follows. The Vz (volume of distribution) of IVIG is approximately 0.05 L/kg, which is approximately the plasma volume.³⁹ At the proposed dose of 0.25 g/kg, a 70 kg subject would receive 350 mL of influenza IVIG (with a minimum HAI titer of 1:640 for H3N2 and 1:160 for influenza B based on the above results). Thus, in a plasma volume of 3.5 L (0.05 L/kg) the minimum resultant HAI titer is estimated to be approximately 1:64 for H3N2 and 1:16 for influenza B.

At the proposed dose, theoretically the following HAI titers would be expected in the recipient (assuming no pre-existing immunity):

- A/ H1N1pdm09 = 1:64
- A/ H3N2 = 1:64
- B= 1:16

Data from seasonal inactivated vaccines indicate that inducing an HAI titer > 1:40 (sero-protection) in immunized individuals should be at least 70% effective in preventing influenza infection. An overview of 12 studies by de Jong et al. found that the median HAI titer protecting 50% of those vaccinated against the virus was 1:28. However, it must be emphasized that protective pre-exposure prophylactic titers and post-exposure disease-modification titers are distinct concepts that do not necessarily harmonize, and the HAI titer actually needed for modifying favorably the course of an established influenza infection is not clear.

Rockman et al demonstrated in an H5N1 model in ferrets that achieving an HAI titer of 1:8 with a hyperimmune IVIG without any other antivirals was sufficient in preventing death if given early in the illness (during fever), and in delaying death if given at the onset of severe disease.⁴³

In the non-randomized plasma treatment study that showed significant mortality benefit associated with convalescent plasma infusion, the HAI in recipients was estimated to be 1:11.7

3 Methodology

INSIGHT 006: FLU-IVIG

3.1 Study Design

INSIGHT 006: FLU-IVIG is a multicenter, double-blind, randomized, placebocontrolled clinical trial comparing treatment with hyperimmune intravenous immunoglobulin (IVIG) versus placebo in hospitalized patients with locally confirmed influenza A or B who have a NEW score ≥ 2. For participants in both assigned treatment groups, the randomized treatment will be administered in addition to SOC treatment. The study will be blinded to participants and to clinical staff other than the site pharmacist.

Study participants will begin to be enrolled in the 2014-2015 influenza season. Enrollment will continue in subsequent influenza seasons until the required sample size is achieved.

3.2 Treatment

The dispensing of study medication will be performed by a site pharmacist unblinded to the treatment assignment. The pharmacist at each clinical site will use normal saline that is approved by their hospital formulary.

Participants assigned to the placebo arm will receive a 500 mL bag of normal saline without any modifications. For those assigned to IVIG, the pharmacist will prepare a bag containing IVIG at a dose of 0.25 g/kg of actual body weight, to a maximum of 24.75 g IVIG (approximately 100 kg), plus as much saline as is needed to reach a total of 500 mL. Detailed instructions for the pharmacist are in the *INSIGHT FLU-IVIG Pharmacy Manual* and the Investigator's Brochure (IB) for IVIG.

It is recognized that the presence of IVIG in normal saline will produce a yellowish coloration and some turbidity to the saline base that will vary depending upon the amount of IVIG product involved. To knowledgeable staff or participants, this appearance could potentially unblind the study medication at the time of administration. Nonetheless, a reasonable effort will be undertaken to keep both the non-pharmacist staff at the clinical site and the study participant blinded to the treatment administered without interfering with safe intravenous infusion policies that may exist at a given institution.

Following procedures used in INSIGHT 005: FLU-IVIG Pilot, in which the blind was effectively maintained, site pharmacists will be instructed to place a colored sleeve or other suitable covering over the 500 ml bag to mask the color of the contents therein, a process similar to what is occasionally done to shield photosensitive medications from light degradation.

In the case of a medical emergency, at the request of the site investigator, the site's study pharmacy staff can provide the participant's unblinded treatment assignment.

All participants will receive SOC treatment. This will be determined by their treating clinician and will not be dictated by this protocol. It is anticipated that SOC will include

an antiviral effective against the circulating strain of influenza. It is further anticipated that this will be oseltamivir in most cases, but use of other antivirals such as zanamivir or peramivir is permitted and will be left to the discretion of the treating clinician.

3.3 Study Objectives

INSIGHT 006: FLU-IVIG

3.3.1 Primary Objective

The primary objective is to compare the clinical status of patients in the IVIG and placebo groups at 7 days of follow-up using an ordinal outcome with 6 clinical states. Specifically, patients will be categorized into one of the following 6 mutually exclusive categories on Day 7:

- 1) death;
- 2) hospitalization in the intensive care unit (ICU);
- 3) non-ICU hospitalization, requiring supplemental oxygen;
- 4) non-ICU hospitalization, not requiring supplemental oxygen;
- 5) not hospitalized, but unable to resume normal activities; or
- 6) not hospitalized with resumption of normal activities.

3.3.2 Secondary Objectives

- a. To compare participants in the IVIG and placebo groups for the following secondary outcomes:
 - Change from baseline to Day 3 in NEW score
 - The ordinal primary outcome assessed at Days 1-7, 14 and 28
 - Number of days hospitalized
 - Composite of mortality or hospitalization at Days 7, 14 and 28
 - Requirement for invasive mechanical ventilation or admission to the ICU (among those not enrolled from the ICU)
 - Mortality
 - Complications of influenza such as bronchitis and pneumonia
 - Percent of patients shedding virus at Day 3
- b. To compare the IVIG and placebo groups for HAI titer levels at Days 1, 3 and 7.
- c. To compare the IVIG and placebo groups for major clinical outcomes in subgroups defined by the following characteristics measured at baseline:
 - Age
 - Gender
 - Race/ethnicity
 - Geographic region (United States, Europe, South America, Australasia)
 - Duration of symptoms prior to enrollment
 - Influenza subtype
 - Type of hospital ward at time of enrollment
 - Production lot of IVIG
- d. To compare the safety and tolerability of the FLU-IVIG and placebo group for:

- Number and percent with grade 3 or 4 adverse events (AEs)
- Number and percent with serious adverse events (SAEs)
- Number and percent with early termination of study treatment
- e. To relate viral load and HAI changes to clinical outcomes and assess whether these potential surrogate markers explain any clinical endpoint difference found.

3.4 Endpoints

The primary endpoint is an ordinal outcome at Day 7 that has 6 mutually exclusive categories:

- 1. death;
- 2. hospitalization in the intensive care unit (ICU);
- 3. non-ICU hospitalizion, requiring supplemental oxygen;
- 4. non-ICU hospitalization, not requiring supplemental oxygen;
- 5. not hospitalized, but unable to resume normal activities; or
- 6. not hospitalized with full resumption of normal activities.

Other endpoints include:

- Change from baseline to Day 3 in NEW score
- The ordinal primary outcome assessed at Days 1-7, 14 and 28
- Number of days hospitalized
- Composite of mortality or hospitalization at Days 7, 14 and 28
- Among those not enrolled in the ICU, requirement for invasive mechanical ventilation or admission to the ICU
- Percent of patients shedding virus at Day 3
- HAI antibody titer changes through Day 7
- Grade 3 and 4 adverse events
- Serious adverse events
- Percent of patients developing bronchitis, pneumonia or other complications through Day 28
- Mortality

3.5 Randomization

Eligible patients will be randomized in a 1:1 ratio to receive either IVIG + SOC or placebo + SOC. Randomization will be stratified by clinical site.

3.6 Sample Size and Statistical Considerations

The planned sample size for the trial is 320 randomized patients. Sixteen of these 320 patients will come from the FLU-IVIG Pilot. A sample size re-estimation will be made after approximately 150 patients have been enrolled.

The following assumptions were made in estimating the required sample size for the trial:

a. The primary analysis will be intention to treat with a proportional odds model that includes indicators for treatment group and indicators for whether the patient was enrolled in the ICU and required oxygen at the time of

randomization. The model will be stratified by geographic region (United States, Europe, South America and Australasia).

- b. Type 1 error is 0.05 (2-sided) and power =0.80.
- c. Patients will be equally allocated to IVIG or placebo.
- d. The clinical status of patients in the control arm at Day 7 will be similar to patients enrolled in the hospital in FLU 003 (see section 2.1 and table below). The estimates from FLU 003 are based on 333 hospitalized patients who were enrolled 7 or fewer days after onset of influenza symptoms and who had a NEW score of 2 or greater at the time of enrollment.
- e. In FLU 003, approximately 64-65% of patients were out of the hospital on Day 7 (sum of 39.0% and 25.8% in table). We assumed that for patients given IVIG this percent could be increased to 74% (about 10 percentage points). We assumed this same proportional improvement (an odds ratio of approximately 1.6) would apply to other category cutpoints on the ordinal scale (an underlying assumption of the proportional odds model). If that were the case, the percentages in each clinical state in the IVIG group that would be realized are shown Table 2.⁴⁴
- f. Based on the FLU-IVIG Pilot, we expect minimal non-adherence to IVIG and missing data at Day 7.

Table 2: Difference that Can Be Detected in the Day 7 Ordinal Outcome

Power = 80%, Alpha = .05 (2-sided) and Sample Size = 320

1 01101 0070,711,0114 100 (2 01	 ., u.i.a. capic c.		
	Day 7 Outcome (%)		
Hierarchical Outcome	Placebo	IVIG	
Death	1.8	1.0	
In ICU	3.6	2.1	
Non-ICU hospitalization, on O2	15.6	9.9	
Non-ICU hospitalization, not on O2	14.1	10.3	
Not back to normal activities	39.0	38.4	
Resumed normal activities	25.8	38.2	
Odds ratio		1.77	

In summary, 320 patients (160 assigned IVIG and 160 assigned placebo) will be randomized. An odds ratio will be computed as a summary measure of the treatment effect. For the above table, this odds ratio is 1.77. This can be interpreted as the average shift over the entire ordinal outcome scale caused by IVIG. An odds ratio greater than one corresponds to a more favorable response for treatment with IVIG as compared to placebo. With the proportional odds model this odds ratio is assumed to be the same for all possible ways of collapsing the 6-category scale into a better versus worse category (e.g., the odds ratio is 1.77 for out of hospital versus in hospital, not in ICU or death versus death or in ICU, etc).

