6.2 Data Monitoring

INSIGHT 006: FLU-IVIG

The trial will be conducted under the direction of the FLU-IVIG study protocol team. Members of the protocol team are listed in Appendix C. The protocol team (except those who prepare the confidential analyses) and all participating investigators will be blinded to interim results. The protocol team will monitor enrollment, follow-up, and adherence to the assigned treatment as determined by the number and percent of participants who complete the infusion of blinded treatment. Follow-up data will be summarized for both treatment groups combined. The protocol team will carry out a sample size re-estimation after approximately one-half of the patients have been enrolled. For this sample size re-estimation, pooled data for the primary endpoint will be used.

The DSMB will review the study prior to initiation and every 6 months thereafter. The DSMB may convene additional reviews as necessary. After each meeting they will recommend continuing the study as planned, modifying the study, or terminating the study.

The DSMB will be asked to recommend early termination or modification only when there is clear and substantial evidence of a treatment difference. As a guideline, the Lan-DeMets spending function analog of the O'Brien-Fleming boundaries will be used to monitor the primary endpoint comparison.^{47,48}

After approximately 50% of patients are enrolled, futility analyses will be presented to the DSMB by the unblinded statisticians based on conditional power estimates. Conditional power incorporates the observed results by treatment group thus far (and uses the originally assumed treatment effect for future data) to calculate the conditional probability of obtaining a significant result by the end of the trial. If conditional power, given the observed data and assuming the originally hypothesized treatment effect thereafter, is less than 10%, consideration should be given to stopping the trial.

7 Protection of Human Subjects & Other Ethical Considerations

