- The subgroup of participants with influenza A infection is identified as a key subgroup for whom the benefit is expected to exceed that of the overall group randomized (i.e., the treatment effect for those with influenza A is expected to be greater than for with influenza B infection) (see section C.). Power is estimated for the subgroup with influenza A.
- Outcomes other than the primary endpoint are divided into key secondary endpoints, supportive efficacy endpoints, and safety endpoints. The three key secondary endpoints are listed in terms of their importance.

B. Protocol summary and history

FLU-IVIG is a randomized, double blind multicenter, international clinical trial. Hospitalized patients with a National Early Warning (NEW) score of 2 or greater will be randomized in a 1:1 allocation ratio to either IVIG plus standard of care (SOC) therapy or to placebo for IVIG (a comparable volume of normal saline) plus SOC, and followed for 28 days. A total of 320 adult patients were to be enrolled over multiple influenza seasons. A schematic of the design is given below.

FLU-IVIG Design
Hospitalized Adults with Influenza A or B

The primary endpoint is an ordinal outcome at Day 7 that has 6 mutually exclusive categories:

1. Death
2. In the intensive care unit (ICU);
3. Non-ICU hospitalization, requiring supplemental oxygen;
4. Non-ICU hospitalization, not requiring supplemental oxygen;
5. Discharged, but unable to resume normal activities; or
6. Discharged with full resumption of normal activities.

Sample size was estimated assuming the following:

- A proportional odds model would be used to compare the IVIG and placebo groups for the primary ordinal outcome.⁴
- Type 1 error of 0.05 (2-sided) and power=0.80 to detect an odds ratio of 1.77 (an odds ratio greater than 1.0 corresponds to a more favorable response to IVIG than placebo).

For the primary analysis, in addition to a treatment indicator, the model will include indicators for whether the participant was enrolled in the ICU or general ward and whether oxygen was required, and will be stratified by geographic region.

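### The treatment effect assumed in protocol 3.6 item e (74% out of hospital, odds ratio about 1.6) is not the effect behind Table 2 and the 80% power (76.6%, odds ratio 1.77).

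*Protocol*

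**What the plan says.** Protocol section 3.6 lists the assumptions behind the sample size. Item b sets the error rates: "Type 1 error is 0.05 (2-sided) and power =0.80". Item e takes 64-65% of FLU 003 patients out of hospital on Day 7 (39.0% + 25.8%) and says: "We assumed that for patients given IVIG this percent could be increased to 74% (about 10 percentage points"). It extends this improvement, "an odds ratio of approximately 1.6) would apply to other category cutpoints on the ordinal scale". On that basis, it continues, "the percentages in each clinical state in the IVIG group that would be realized are shown Table 2".

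Table 2 is headed with 80% power, two-sided alpha 0.05 and 320 patients. Its IVIG column ends with 38.4% discharged but not back to normal and 38.2% back to normal, and its last row gives an odds ratio of 1.77. The paragraph after the table applies that value to the cutpoint discussed in item e: "the odds ratio is 1.77 for out of hospital versus in hospital".

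The SAP, section I.B, restates the design as "Type 1 error of 0.05 (2-sided) and power=0.80 to detect an odds ratio of 1.77". SAP Table 1 repeats the Table 2 percentages.

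Protocol section 6.2 describes a futility analysis by conditional power that "uses the originally assumed treatment effect for future data". It asks that stopping be considered if conditional power, "assuming the originally hypothesized treatment effect thereafter, is less than 10" percent. It gives no number for that effect.

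**The concern.** Item e and Table 2 give two different effects for the same outcome, in the same arm, at the same cutpoint, and the text says that one produces the other. The three figures in item e (74%, about 10 points, about 1.6) agree with one another and disagree with the table.

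Two things are at stake. First, someone who reads item e together with item b would conclude that the trial has 80% power for a 10-point gain in patients out of hospital. If it does not, a null result says less about a benefit of that size than the protocol implies. Second, section 6.2 refers back to the assumed effect without stating it, so section 3.6 offers two candidates for the conditional-power calculation.

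**Working it through.** **Inputs.** All are from protocol 3.6 and Table 2: placebo percentages 1.8 / 3.6 / 15.6 / 14.1 / 39.0 / 25.8 (death to back to normal; sum 99.9, rescaled to 100), N = 320 allocated 1:1, two-sided alpha 0.05, power 0.80. The method is the Whitehead ordinal sample-size formula, cited in both documents. It is applied without covariate adjustment.

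**1. Formula.** The IVIG column is the placebo column shifted by a common odds ratio (OR) at every cutpoint. With p̄ the mean of the two arms in each category,

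N = 12 (z₀.₉₇₅ + z₀.₈₀)² / [(ln OR)² (1 − Σp̄³)], where 12 × (1.960 + 0.842)² = 94.19.

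Power at N is Φ(θ − 1.960), with θ = ln OR × √[N (1 − Σp̄³)/12].

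**2. Reproducing the plan's figure (OR 1.77).** The shifted IVIG column is 1.0 / 2.1 / 9.9 / 10.4 / 38.4 / 38.1, which matches Table 2 to within 0.1. With ln OR = 0.571 and 1 − Σp̄³ = 0.905, N = 94.19 / (0.326 × 0.905) = 319. At 320, θ = 2.805 and power = Φ(0.845) = 0.80. The stated 320 is reproduced.

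**3. Odds ratios in Table 2 as printed.** Out of hospital: (0.766/0.234) / (0.648/0.352) = 3.274 / 1.841 = 1.78. From the death cutpoint upward, the five values are 1.81, 1.78, 1.78, 1.78 and 1.78. The table is internally consistent with 1.77, allowing for rounding.

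**4. Odds ratios implied by item e.**
- 64% to 74%: (0.74/0.26) / (0.64/0.36) = 1.60
- 64.8% to 74.8% (exactly 10 points): 1.61
- 64.8% to 74%: 1.55
- 65% to 74%: 1.53

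The widest reading allowed by rounding runs from odds(0.735)/odds(0.65) = 1.49 to odds(0.745)/odds(0.64) = 1.64. It does not reach 1.77.

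**5. What Table 2 would show under OR 1.6.** The IVIG column would be 1.1 / 2.3 / 10.8 / 11.0 / 38.9 / 35.8, with 74.7% out of hospital instead of 76.6%.

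**6. Power under each effect.**

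| Effect | OR | N for 80% power | Power at 320 |
|---|---|---|---|
| Table 2: 64.8% to 76.6% | 1.77 | 319 | 0.80 |
| 10 points: 64.8% to 74.8% | 1.61 | about 456 | 0.65 |
| Item e: OR about 1.6 | 1.60 | 470 | 0.64 |
| 64.8% to 74% | 1.55 | about 547 | 0.57 |
| 65% to 74% | 1.53 | about 568 | 0.56 |

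A simulation of 4,000 rank-sum tests per scenario gave 0.80, 0.64 and 0.57 for OR 1.77, 1.6 and 1.545. Other sizing conventions do not bring item e to 320 either. At OR 1.6, one-sided alpha gives 370 and a control-arm-only variance gives 465. A two-proportion test of 64.8% against 74% needs 786.

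**7. Conditional power at half information (t = 0.5).** CP = Φ{[Z√t + θ(1 − t) − c] / √(1 − t)}, with final critical value c = 1.96 and θ = 2.805 (OR 1.77) or 2.312 (OR 1.6). CP falls below 10% at Z = −0.49 under 1.77 and at Z = −0.14 under 1.6. At Z = −0.30, CP is 0.138 or 0.075, on opposite sides of the threshold. The width of the disputed interval is (2.805 − 2.312) × 0.5/√0.5 = 0.35 in Z and does not depend on c.

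**The case against.** The best defence is that 1.77 is plainly the operative value. Item e is the only place where 74% or 1.6 appears. Table 2 is titled as the detectable difference and follows item e directly. The SAP calls 1.77 the value specified in the protocol, used it for the August 2017 re-estimation, and repeats it in sections I.B, C and G. On this view nobody would have run conditional power at 1.6, and the mismatch is loose wording. This identifies which figure drove the sample size. It does not rescue item e, which says that Table 2 follows from its own assumption. Had two effects been intended, one expected and one detectable, the text would need to say so and give the power for each.

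Three narrower points have some force:

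- **Final critical value.** Section 6.2 names O'Brien-Fleming-type spending, so the final value would exceed 1.96. If two to seven equally spaced looks are assumed, it is about 1.97 to 2.06, and the interval of disagreement moves from (−0.49, −0.14) to between (−0.48, −0.13) and (−0.35, 0.00). The limits are therefore illustrative; the 0.35 gap remains.
- **Timing.** The futility guideline is advisory, and the SAP records the last enrolment in May 2018 and the last DSMB meeting in January 2018. Naming the effect in section 6.2 now completes the record and alters no decision.
- **The 470 figure.** An OR of 1.6 needs 470 patients, the same number as the contingency in protocol section 3.7. Item e may belong to that scenario. The documents do not say so, and the match is only suggestive.

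**Conclusion.** The point holds. Item e does not generate Table 2, and neither rounding nor the word approximately closes the gap. With 320 patients the trial has 80% power for an odds ratio of 1.77 (64.8% to 76.6%, about 12 points). It has about 0.64-0.65 for a 10-point gain and 0.56-0.57 for a rise to exactly 74% from 64.8-65%. These figures assume proportional odds, the FLU 003 control percentages and no covariate adjustment. The formula that reproduces 320 also ignores the planned adjustment for baseline ICU and oxygen status and for region.

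The sizing itself is sound at 1.77, and Table 2, the target power and the SAP agree with one another. The error is confined to the assumption written in item e and its link to the table, with a secondary ambiguity in section 6.2. It should be fixed because it misstates the effect to which the power claim applies.

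**What to change.** - **Protocol 3.6, item e:** state the effect actually powered, 64.8% to 76.6% out of hospital (about 12 points), with an odds ratio of 1.77 at every cutpoint.
- **Beside it, as two separate figures:** with 320 patients, unadjusted power is about 0.64-0.65 for a 10-point gain (odds ratio 1.60-1.61) and about 0.56-0.57 for 74% from 64.8-65% (odds ratio 1.53-1.55). Note that covariate adjustment is ignored.
- **Protocol 6.2:** name the odds ratio of 1.77 as the effect assumed for future data in the conditional-power calculation.

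The cost is a few lines of wording. Enrolment, alpha, the primary model and the SAP's re-estimation are unchanged. The protocol would then openly show less favourable power for a 10-point gain than a reader of item e would infer.
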